### 3.5 Adverse Events

The OHRP defines an adverse event as “any untoward or unfavorable medical occurrence in a human subject, including any abnormal sign, symptom, or disease, temporally associated with the subject’s participation in the research.” Adverse events can additionally be classified as an unanticipated problem, meaning it was not expected to occur during the course of the research. If an unexpected adverse event were to occur, it then needs to be determined whether or not it is due to the research being conducted. If the event is a result of the research procedures, most likely the event is directly connected to the subject’s participation in the research. It is also vital to determine whether an adverse event is serious. The OHRP defines a serious adverse event as one that a) results in death, b) is life-threatening, c) results in patient hospitalization or prolongation of existing hospitalization, d) results in persistent or significant disability/incapacity, e) results in congenital anomaly, or f) jeopardizes the subject’s health to the point where they may need medical or surgical intervention. If the adverse event is unexpected, related to the research, and serious (where it is causing harm to subjects), then it is also classified as an unanticipated problem and must be reported to the Thomas Jefferson University Hospital IRB. All adverse events will be reported in accordance with Jefferson IRB Adverse Events Report. The IRB shall be notified in a written safety report if any serious and unexpected adverse

experience associated with the use of the oral or intravenous nutritional supplements occurs.

### 3.6 Data Collection and Submission Schedule

3.6.1 Data Submission: Data must be submitted according to the protocol requirements for all subjects registered, whether or not assigned treatment is administered.

3.6.2 Master files, such as case report forms and progress reports, are monitored by the study coordinator, [name]. Case report forms will include eligibility checklist, demographic data, baseline history, adverse events, and off-study documents. These will be completed by study staff under the supervision of the investigators or the project manager.

### 3.7. Clinical Response

Subjects will be evaluated utilizing the UPDRS scores to determine any improvements in PD symptoms. Subjects will also be evaluated using the Profile of Moods Scale, Beck Depression Inventory, Mini-Mental Status Exam, and Parkinson's disease Questionnaire-39. These will be obtained initially and after approximately 90 days of taking the supplements.

#### 3.7.1 SPECT Imaging Procedure

(a) Subject Preparation - An indwelling catheter needle will be inserted into an antecubital vein. DaTSCAN will be administered through the indwelling line.

(b) DaTSCAN SPECT Imaging Procedure – Subjects will receive a standard of care DaTScan initially and after completing the NAC regimen. Subjects will be asked to arrive at the Nuclear Medicine SPECT Center on the day of the study. A signed informed consent form will be documented after all questions have been answered. Women of childbearing potential must have had a negative pregnancy test within 48 hours before proceeding with the SPECT study. The intravenous catheter will be inserted and capped. Approximately 30 minutes prior to injection of the DaTSCAN, the patient will be given an oral dose of lugol's solution, which is the standard of care for these scans. Lugol's solution helps to protect the thyroid from additional radioactive exposure from the DaTSCAN tracer. DaTSCAN (4-5 mCi,  $\pm 20\%$ ) will be injected intravenously. After injection of the DaTSCAN, the venous catheter will be removed, and then the subject permitted to get off the examination table. Subjects can then take a break for lunch. Subjects will receive an MRI to assist with anatomic delineation. In addition, the MRI session will be utilized in order to obtain data via MR Spectroscopy (MRS), which can provide a measure of various metabolites, such as glutathione, in specific brain structures (please see below).

(c) Image Acquisition and Processing - The dose of DaTSCAN will be injected in an antecubital vein, and SPECT images acquired at approximately 3 hours post injection for about one hour. This will enable us to obtain quantitative regional uptake values as determined by our previously described reference region method. All scans will be performed on a Philips Forte gamma camera or equivalent camera equipped with ultra-high resolution collimators. All the images will

be reconstructed using filtered back projection. Chang's first order correction method is used to compensate for photon attenuation.

Manual demarcation of brain regions - A set of standardized templates containing small ROIs will be fit on each DaTSCAN. Within the x-y plane, small ROIs in the template will be smaller than the actual structures they represent in order to minimize resolution-induced problems with ill-defined edges. To reduce the effects of volume averaging in the axial direction, the small ROIs will not be placed on the slices that contained the upper most and lower most portions of the structures they represent. This will tend to limit the small ROIs to the central aspect of structures they represent. The primary outcome measure will be the specific uptake values at 3 to 4 hours post administration, when the distribution of DaTSCAN has approached a transient, near equilibrium like state that reflects the ratio of  $k_3/k_4$ , which is related to binding potential. This allows for a quantitative assessment of dopamine transporter activity. Again, scanning at this time of a pseudo-equilibrium state allows for quantitative analysis using a region of interest analysis with a background region as an index of nonspecific binding.

As described above, it is probably not necessary to account for volumetric changes especially since the ROIs will be smaller than the actual structures. However, since all scans will have MRI correlation for adequate placement, volumes of the basal ganglia structures can be determined and utilized as an additional analysis. The reference region has typically been the cerebellum or the brain regions above the level of the basal ganglia, corresponding to areas of the brain, which have very low concentrations of DAT. However, values will be obtained for both whole brain regions above the basal ganglia and cerebellar regions in order to confirm the findings.

Statistical Parametric Mapping (SPM) will also be performed on the images in order to compare the pre- and post-intervention scans in PD subjects. SPM is currently considered to be a highly successful analytical tool for evaluating of SPECT brain images, and will be included in the analysis.

### 3.7.3 MR Spectroscopy Procedure

A brain proton magnetic resonance spectroscopic imaging ( $^1\text{H}$  MRS) will be performed in the Department of Radiology at Thomas Jefferson University and Hospital over approximately one hour. The sections of the brain scanned will be oriented obliquely along the AC/PC line. Cortical and subcortical structures such as the basal ganglia will be evaluated for the following metabolites: glutathione; N-acetylaspartate (or NAA, an indicator of neuronal integrity), creatine+phosphocreatine (CR, important in cell energetics), choline (CHO, involved in cell membrane biosynthesis/degradation), and lactate (LAC, end product of glycolysis or anaerobic metabolism). Statistical Parametric Mapping will be used to determine the differences in the concentrations of the various metabolites before and after receiving intravenous/oral NAC. In addition, connectivity and resting cerebral blood flow can be measured during the same imaging session.

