## **2.0 OBJECTIVES**

- 2.1 Evaluate Nutritional Supplementation with intravenous/oral NAC.
  - 2.1.1 To evaluate if oral supplementation or intravenous/oral NAC as described below helps to support dopamine function in the brain of patients with PD by measuring clinical symptoms.
  - 2.1.2 To evaluate whether intravenous/oral NAC helps to support dopamine function in the brain of patients with PD by measuring changes in the dopamine transporter using DaTScan SPECT imaging.
  - 2.1.3 To evaluate whether intravenous/oral NAC as described below helps to support changes in oxidative stress and metabolism, as measured by magnetic resonance spectroscopy (MRS), in patients with PD.

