*Significance assessment.* The statistical parametric maps represent significant differences at the pixel-level. However, in a typical brain image, there are many thousands of pixels, and the probability that many of them will be significant purely by chance is high, even for tight thresholds. The final step in SPM assesses the significance of *clusters* of suprathreshold pixels, correcting for the effects of such a large number of correlated multiple comparisons using the theory of random Gaussian fields. Statistically significant differences between and baseline and post-treatment scans will be assessed at each voxel with a threshold of  $P < 0.001$ . To correct for correlated multiple comparisons, clusters of voxels which survive this threshold will be assessed further using the theory of random Gaussian fields (67,68), which calculates the significance of clusters based on their peak height and spatial extent. Due to the limited volume of the striatum, the small volume correction will be used within SPM, allowing a more sensitive test. With this technique, differences in DaTSCAN binding between baseline and post-treatment scans will be assessed, and statistic images generated showing significant regional differences. A correlational analysis with various neuropsychological parameters such as the UPDRS, profile of mood scale, and Parkinson's Disease Questionnaire will also be performed with SPM. Similar analysis will be performed for the MRS data, which will compare the concentration of the specific molecules measured by MRS before and after three months of the nutritional supplementation program.

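### Five unranked MRS metabolite maps serve objective 2.1.3, and the plan's only multiplicity correction works within one map, not across the five

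*Combined protocol and SAP*

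**What the plan says.** Section 2.0 sets objective 2.1.3: to evaluate by MRS whether NAC "helps to support changes in oxidative stress and metabolism". It names no metabolite, no region and no rule for reading the result.

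Section 3.7.3 gives the measurements: "Cortical and subcortical structures such as the basal ganglia will be evaluated for the following metabolites: glutathione; N-acetylaspartate". The list goes on through creatine plus phosphocreatine to "choline (CHO, involved in cell membrane biosynthesis/degradation), and lactate (LAC, end product of glycolysis or anaerobic metabolism", five metabolites in all. On analysis it says "Statistical Parametric Mapping will be used to determine the differences in the concentrations of the various metabolites before and after receiving" NAC. No metabolite is ranked above another.

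Section 3.8.3 holds the only multiplicity control in the plan. For the DaTSCAN images, "Statistically significant differences between and baseline and post-treatment scans will be assessed at each voxel with a threshold of" P<0.001. Surviving clusters are then assessed, "correcting for the effects of such a large number of correlated multiple comparisons using the theory of random Gaussian fields", with a small volume correction for the striatum. The method is carried over to spectroscopy: "Similar analysis will be performed for the MRS data, which will compare the concentration of the specific molecules measured by MRS". No cluster-level or map-level alpha is given. The same section plans a further set of SPM maps: "A correlational analysis with various neuropsychological parameters such as the UPDRS, profile of mood scale" and the Parkinson's questionnaire.

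Elsewhere, section 3.7.1 makes DaTSCAN specific uptake the primary outcome measure. Section 1.6 presents MRS as a supplementary biomarker, and section 3.8.4 describes the study as primarily a pilot.

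**The concern.** Random-field theory answers one question: given many correlated voxels in a single statistic image, how likely is a cluster this high or this large by chance? It has no bearing on how many separate images are examined. With five metabolites there are five images, each with its own opportunity for a false positive, and nothing in the plan adjusts across them.

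The gap is easy to miss because section 3.8.3 presents the random-field step as the remedy for multiple comparisons. A cluster in the lactate or choline map could be taken as fully corrected when the correction stopped at the edge of that map.

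What is at stake is how objective 2.1.3 is read. Suppose one metabolite changes and glutathione does not. The plan does not say whether that is evidence on the objective, a lead to follow up, or the kind of finding expected by chance when five maps are inspected. For a pilot meant to inform larger trials, the risk is carrying forward a metabolite that was picked by chance.

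**Working it through.** The plan gives no family-wise error figure for MRS, so there is none to reproduce. The sample-size calculation in section 3.8.4 concerns DaTSCAN binding and does not enter here.

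**Inputs**
- Number of maps: 5 (glutathione, NAA, creatine, choline, lactate), from section 3.7.3.
- Error rate per map: two-sided 0.05. This is an assumption. Section 3.8.3 gives only the voxel threshold of 0.001, and 0.05 appears only in the sample-size paragraph of section 3.8.4.
- Correlation between metabolite test statistics: not in the documents. Values of 0, 0.3, 0.5 and 0.8 are assumed to show the range.

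**Why 0.001 is not the per-map rate.** It applies to each voxel and serves to form clusters. Section 3.8.3 itself notes that an image has many thousands of pixels, so the error rate of a map is set by the cluster step, whose alpha is missing.

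**Independent maps**
- P(at least one false positive) = 1 − (1 − 0.05)^5 = 1 − 0.7738 = 0.226.

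**Correlated maps.** Simulation of 400,000 sets of five equicorrelated standard normal statistics with no true change, counting sets in which any absolute value exceeds 1.96:

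| Correlation | P(at least one false positive) | Multiple of 0.05 |
|---|---|---|
| 0 | 0.226 | 4.5 |
| 0.3 | 0.209 | 4.2 |
| 0.5 | 0.182 | 3.6 |
| 0.8 | 0.127 | 2.5 |

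**Sensitivity to the missing alpha.** If the map-level rate were 0.01, the independent figure would be 1 − 0.99^5 = 0.049. The size of the problem therefore depends on a number the plan leaves out.

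**After the change**
- Glutathione as a single pre-named map at 0.05: error 0.05.
- The other four under Holm at 0.05: the smallest p-value is compared with 0.05/4 = 0.0125. If independent, the chance of any false positive among the four is 1 − 0.9875^4 = 0.049.
- These are two families. Together the chance of any false positive is 1 − 0.95 × 0.9875^4 = 0.097 if independent, and at most 0.05 + 0.05 = 0.10. Testing the four only after glutathione is significant would bring the total back to 0.05.

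**The case against.** The strongest reply is that no confirmatory claim is planned for MRS. DaTSCAN uptake is the primary outcome measure, section 3.8.2 covers DaTSCAN binding and clinical scores for the primary objectives, MRS is supplementary, and the study is meant to estimate effects for later trials. On that view, family-wise control over non-primary biomarkers is a matter of taste. This stands as a reason for low severity. It does not remove the point: 2.1.3 is a listed objective, section 3.8.3 declares significance by threshold and correction, and nothing labels the MRS maps exploratory or says how one positive map among five is to be read.

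A reader might also infer more than the documents support:

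- *That cortical and subcortical structures multiply the number of tests.* In one whole-map SPM analysis, the random-field step already covers structures within the map. The plan neither says that structures are tested separately nor gives their number. The count is five.
- *That each map is tested at 0.05.* No map-level alpha is stated, so this can only be assumed.
- *That the clinical-score correlation maps add to the error on 2.1.3.* They address association with symptoms, and their sentence follows the DaTSCAN comparison. They are a separate family and do not bear on that objective.
- *That a chance finding would meet 2.1.3.* The objective is to evaluate, and it has no pass rule to meet.
- *That basal-ganglia glutathione should be the sole answer.* The objective also covers metabolism, to which creatine and lactate speak. Section 1.6 cites a treatment-related choline/creatine change in motor cortex and calls basal-ganglia findings inconclusive. The case for glutathione in sections 1.1 and 1.3 concerns the brain in general.

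**Conclusion.** The point holds in limited form. The plan compares five unranked metabolite maps for objective 2.1.3 and corrects for multiplicity only within each map. If each map is controlled at two-sided 0.05 and no metabolite changes, the chance of at least one false-positive metabolite is about 0.23 under independence, 0.18 at correlation 0.5 and 0.13 at 0.8. Both the 0.05 and the correlations are assumptions. That the correction does not reach across maps follows from the method and needs neither.

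This is a low-severity, inexpensive improvement. It leaves the primary outcome, the sample size and the conduct of the study untouched, and changes only what may be concluded from MRS.

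**What to change.** In sections 3.7.3 and 3.8.3:

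1. State the map-level (cluster) alpha, and say that the random-field and small-volume corrections apply within one map only.
2. Name brain glutathione in advance as the lead MRS result for the oxidative-stress part of objective 2.1.3, tested at that alpha, with the region chosen by the sponsor before any data are analysed. The plan's own rationale supports this choice: section 1.1 says that NAC raises brain glutathione, and section 1.3 cites a mean maximal rise of 55% in patients with PD.
3. Holm-adjust NAA, creatine, choline and lactate across the four, or label them exploratory. If one overall 5% limit across all five is wanted, test the four only after glutathione is significant.
4. As a separate minor matter that does not bear on 2.1.3, label the SPM correlations with UPDRS, mood and questionnaire scores hypothesis-generating.

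The cost is a few sentences, with no new data or patients. The downside is that a lone change in a metabolite other than glutathione could not be reported as a stand-alone positive, and under Holm the four would have less power. The documents give no MRS variability, so that loss cannot be quantified.

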## 1.6 Utilizing Magnetic Resonance Spectroscopy (MRS) to measure changes in the chemical milieu in brain of PD patients

It will also be beneficial to assess whether there are specific changes in levels of different molecules that are related to energy consumption and oxidative stress. Proton MR spectroscopy (1H-MRS) has been previously performed in Parkinson's disease (PD) and parkinsonian syndromes to evaluate in vivo concentrations of basal ganglia and cerebral cortex metabolites such as N-acetylaspartate (NAA), choline (Cho), and creatine (Cr) (55). This technique has been used to evaluate both the basal ganglia and motor cortex in PD patients (56,57). For example, one study showed a significant reduction in the NAA/Cr ratio in the motor cortex of PD patients compared with controls. Other studies have revealed inconclusive findings in the basal ganglia in PD patients. However, several studies have observed changes in MRS in PD patients in response to therapy. For example, one study demonstrated that after 6 months of therapy with pergolide, PD patients showed an improvement in motor performances and an increase in Cho/Cr ratios in

the motor cortex (58). The authors concluded that dopaminergic therapy capable of improving motor function might restore the Cho/Cr ratio in the motor cortex. While there are no MRS studies of glutathione concentrations in PD patients, the glutathione level is associated with the level of oxidative stress and has been measured in several other pathological conditions such as head trauma, stroke, and Alzheimer's disease (59,60,61). Thus, we plan to include MRS as an additional biomarker to evaluate the potential effects of the nutritional supplements and/or NAC on oxidative stress and cerebral activity in PD patients.

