## 3.8 Statistical Considerations

**3.8.1 Descriptive and Exploratory Analyses:** The initial analyses of the data will be descriptive in nature. Using means, standard deviations, median, and range, the distribution volume ratios (DVRs) will be described for each time point before and after subjects have used the nutritional supplementation for approximately 90 days. Similarly, the clinical scores will be described for each time point. Graphical methods, such as plots of measurements over time, histograms, and boxplots are important tools for understanding the quality of the data, and assessing assumptions underlying statistical models (such as normality). Transformations will be applied as necessary to satisfy these assumptions. Plots of all of the measured variables over time will be important to assess longitudinal patterns of change.

**3.8.2 Analyses for Primary Objectives:** To evaluate whether intravenous/oral NAC helps to support dopamine function in the brain of patients with PD by measuring changes in the dopamine transporter. To accommodate the longitudinal nature of the data, a Heterogeneous Random Coefficients Model (62,63) will be fit for the DVRs in each region for the DaTSCAN binding and each neurobehavioral score (i.e. UPDRS scores). This model can also account for both between and within subject heterogeneity and will accommodate modeling potentially nonlinear therapeutic effects over time. The random coefficients model is more flexible in terms of modeling the changes in DVRs and neuropsychological tests over time than repeated measures analyses of variance. The random coefficients model also has fewer restrictions on the correlation structure between multiple measures within subjects. ANCOVA will be used in order to determine if there are correlations between the pre-intervention neuropsychological and clinical measures and the longitudinal outcome measures after receiving oral or intravenous supplementation. This analysis will also evaluate whether the DaTSCAN DVRs can be utilized as a predictor for outcome. To determine if there is a correlation between changes in DAT binding and symptom severity, Pearson product-moment correlations will be computed unless the normality assumption is violated, in which case the Spearman rank correlation will be computed.

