**3.8.4 Power Analysis:** We view this study primarily as a pilot study to assess changes in physiological and clinical measures and determine the effect size for powering future, larger trials. However, we estimated the sample size needed based upon prior research we have performed evaluating DAT imaging in the study of PD patients. We have previously found that the PD patients can have variability in their DVR measures of dopamine binding of approximately 10%. If we expect a 5-10% improvement in the treatment groups, for an 80% power to detect a significant change of  $p=0.05$ , we would need approximately 28 subjects in the treatment arms and approximately 14 subjects in the control arm. The statistical analyses for the proposed study will consist of 1) repeated measures two-way ANOVA, and 2) linear regression. Both methods are more powerful than simple t-tests on which these estimates are based. Thus, we plan to recruit up to 65 subjects, to allow for attrition which could be as high as one third, who would then be randomized into the two groups in a 2:1 ratio until the groups are complete.

3.8.5 Randomization: Randomization will occur via a 2:1 ratio of the NAC group and the waitlist control groups using the method of random permuted blocks with random block sizes without stratification.

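### Every stated MRS and SPM comparison is before versus after with no arm term, so objective 2.1.3 has no specified NAC-versus-waitlist test in a randomised trial

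*Combined protocol and SAP*

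**What the plan says.** Objective 2.1.3 (section 2.0) is to learn whether intravenous/oral NAC "helps to support changes in oxidative stress and metabolism, as measured by magnetic resonance spectroscopy (MRS), in patients with PD". Sections 3.8.4 and 3.8.5 randomise subjects 2:1 to NAC or a waitlist control.

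The MRS analysis is stated twice:
- Section 3.7.3: "Statistical Parametric Mapping will be used to determine the differences in the concentrations of the various metabolites before and after receiving intravenous/oral NAC".
- Section 3.8.3, under significance assessment: a similar analysis to that for the DaTscan images, "which will compare the concentration of the specific molecules measured by MRS before and after three months of the nutritional supplementation program".

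The voxel-wise comparison of DaTscan images is stated in the same form:
- Section 3.7.1: SPM is run "in order to compare the pre- and post-intervention scans in PD subjects".
- Section 3.8.3: "differences in DaTSCAN binding between baseline and post-treatment scans will be assessed", with a voxel threshold of P < 0.001 followed by cluster assessment and a small volume correction.

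Two other passages bear on the point. The random coefficients model in section 3.8.2 "will be fit for the DVRs in each region for the DaTSCAN binding and each neurobehavioral score"; metabolites are not listed. Section 3.8.4 says: "The statistical analyses for the proposed study will consist of 1) repeated measures two-way ANOVA, and 2) linear regression". It names neither the factors nor the outcomes. Section 1.6 gives MRS a supporting role: "we plan to include MRS as an additional biomarker".

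**The concern.** A before-and-after comparison answers whether the marker changed, not whether NAC changed it. Over 90 days a metabolite concentration or a tracer ratio can move through disease course, scanner or session effects, regression to the mean, or a change in antiparkinsonian medication, which section 3.3.1 lets the referring neurologist make. The randomised waitlist arm is there to remove these influences, and the stated MRS and SPM contrasts do not use it. Read literally, the sentence in section 3.7.3 does not apply to waitlist subjects at all, since they receive no NAC in the comparison period.

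The stake is how objective 2.1.3 is answered, and what is carried forward. Section 3.8.4 describes the study as a pilot meant to supply effect sizes for larger trials. A within-arm change reported as the NAC effect on glutathione would pass any time trend into that planning.

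**Working it through.** **Step 1. Does any text supply a between-arm test for MRS or the maps?**

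| Text | Covers MRS? | Covers the maps? | Arm term named? |
|---|---|---|---|
| 3.7.1, SPM sentence | no | yes | no, pre v post |
| 3.7.3 | yes | no | no, before v after |
| 3.8.1, descriptive summaries and plots | plots only | no | no |
| 3.8.2, random coefficients model | no | no | no |
| 3.8.2, ANCOVA of baseline measures against later outcomes | not named | no | no |
| 3.8.3, comparison sentences | yes | yes | no, before v after |
| 3.8.3, SPM correlation with clinical scales | no | yes | no |
| 3.8.4, two-way ANOVA and linear regression | not stated | not stated | factors not stated |

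One sentence in 3.8.3 is garbled just where a group might have been named, but a later sentence in the same section repeats baseline versus post-treatment cleanly. Only the general line in 3.8.4 could reach MRS with a group comparison, and it does not say so.

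**Step 2. Inputs for an illustration.** The plan gives no sample size, variability or expected effect for MRS, so there is no plan figure to reproduce on this point. The 28 and 14 in section 3.8.4 were derived for DVRs. They are numbers after attrition: 42/(1 − 1/3) = 63, consistent with recruiting up to 65. I take n = 28 (NAC) and 14 (waitlist), two-sided tests (an assumption; sidedness is not stated), and the SD of 90-day change as the unit. The shifts are assumptions, equal in both arms; the documents give none.

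**Step 3. False rejection when NAC does nothing.** For the paired test the noncentrality is shift × √28 with 27 df, and critical values are 2.052 (0.05) and 3.690 (0.001).

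| Common shift (SD) | Noncentrality | Rejects at 0.05 | Rejects at 0.001 |
|---|---|---|---|
| 0.1 | 0.53 | 8.0% | 0.3% |
| 0.2 | 1.06 | 17.5% | 1.0% |
| 0.3 | 1.59 | 33.4% | 3.2% |
| 0.4 | 2.12 | 53.2% | 8.4% |

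In the two-sample test on change scores a common shift cancels. In 200,000 simulated trials it rejected 5.0% of the time at 0.05 and 0.1% at 0.001, for shifts of 0.1 and of 0.4 SD. The 0.001 column is a single test; the cluster and small-volume steps are not modelled.

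**Step 4. Direction for DAT.** Section 1.4 describes DAT as declining, faster in PD. With a true benefit of 0.5 SD and drift of 0, −0.2 or −0.4 SD, single-voxel pre-post power at two-sided 0.001 is 18%, 3% and 0.2%. Decline hides a benefit; it does not create one. For MRS no direction is given.

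**Step 5. Precision of the two contrasts.**
- SE: pre-post √(1/28) = 0.189; between arms √(1/28 + 1/14) = √(3/28) = 0.327; ratio √3 = 1.73.
- 95% CI half-width: pre-post 2.052 × 0.189 = 0.39 SD; between arms 2.021 × 0.327 = 0.66 SD.
- Difference detectable with 80% power at 0.05: 0.55 SD pre-post; 0.94 SD between arms.
- Baseline adjustment multiplies the between-arm SE by √((1 + ρ)/2), assuming equal variances, with 39 df: 0.81, 0.87 and 0.92 SD for assumed ρ = 0.5, 0.7 and 0.9.
- Single-voxel power at 0.001 for 0.5 and 1.0 SD: 18% and 93% pre-post; 3% and 33% between arms.

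**The case against.** The best reply is that a controlled test is already there. Section 3.8.4 speaks for the whole study, and with two arms and two time points a repeated measures two-way ANOVA is most naturally group by time. The linear regression could also carry an arm term. This is a fair reading, and it rules out a stronger inference that a reader might draw, namely that the waitlist data will go unused. The documents do not show that. What stands is that the line sits in the power section, names no factor or outcome, and is not tied to MRS or the maps, whose own sections state a different contrast.

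A second reply is that the weight is small: the study is a pilot, MRS is an additional biomarker, and SPM supplements the regional analysis. That limits the severity, but 2.1.3 is still one of three listed objectives.

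Third, the shifts are assumed and the true ones may be near zero. That is correct; at 0.1 SD the false rejection rate at 0.05 is only 8%.

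Fourth, a reader might infer from sections 3.3.1 and 3.7.1 that waitlist subjects are not rescanned, because follow-up imaging is tied there to supplements or the NAC regimen. The documents as a whole do not support this. Section 3.1 has the waitlist group evaluated at entry and about 90 days later, section 3.4.1 measures endpoints in both arms, and section 3.8.4 sizes a control arm on DVRs. The wording needs reconciling; it is not evidence that scans are missing.

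**Conclusion.** The point holds and should be fixed. For MRS and the SPM maps the plan states a contrast that cannot separate NAC from time trends or permitted medication changes, and no text specifies a between-arm test for them. This is more than missing detail, because a contrast is stated and, followed as written, it gives an uncontrolled answer to objective 2.1.3.

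The size of the bias cannot be derived from the documents. The range of 8% to 53% false rejection at two-sided 0.05 (0.3% to 8.4% at 0.001) rests on assumed common shifts of 0.1 to 0.4 SD, 28 analysed NAC subjects, normally distributed changes and a single test.

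Two wider readings should be resisted. The point does not show that the main regional DVR analysis is uncontrolled; that model is a separate matter. Nor does it suggest that the maps will produce a false DAT benefit, since the only drift the documents describe runs the other way.

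**What to change.** - **3.7.3 and 3.8.3, MRS:** make the NAC-versus-waitlist difference in 90-day change the inferential contrast, adjusted for baseline, with a 95% CI for each metabolite.
- **3.8.3, SPM (and the matching sentence in 3.7.1):** compare per-subject change images between arms and label the result exploratory.
- **Both:** keep within-arm before-and-after results as description.
- **3.8.4:** state that the ANOVA factors are arm and time and that it covers MRS.
- **3.3.1 and 3.7.1:** reconcile the NAC-only follow-up wording with 3.1, 3.4.1 and 3.8.4, so that the documents say plainly whether waitlist subjects have the second SPECT and MRS.

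If paired waitlist scans are planned, as the documents imply, the cost is wording and a different design matrix. The real price is precision. Intervals for MRS widen by about 70% before adjustment, and a difference must approach 0.8 to 0.9 SD of change to be detected with 80% power. Estimates with intervals should therefore lead the report. At the map threshold, between-arm power is too low for a null map to mean much. If waitlist rescans turn out not to be planned, the contrast would need them in about 14 subjects.
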